3.2 Final statistical analysis plan

The primary outcome for efficacy is the rate of symptomatic CSDH ipsilateral recurrences requiring reoperation within 6 months. The statistical analysis for efficacy will be performed according to both the ITT and PP principles. The ITT analysis will be performed using the full analysis set, defined as all randomized patients in the groups allocated by randomization. No exclusions other than those caused by missing information will be made. No imputation will take place. The PP analysis will be performed on the subset of the full analysis set that is compliant with the protocol, has completed treatment, has available measurements, and has no major protocol violations or entry criteria violations.

As the goal of CSDH surgery is not only to prevent reoperations but also to improve neurological function and prevent death, the entire therapeutic effect (value) of intraoperative irrigation (versus no irrigation) may not be sufficiently comprehensively captured by analysing the primary outcome (rate of reoperations) only. For example, any possible between-group differences in the incidences of deaths and unfavorable functional outcomes may have an effect on the likelihood of a patient being considered for reoperation (i.e., skew the primary analysis).

Prompted by this realization, we deemed it necessary to somehow take into account between-group differences in either mortality and/or unfavorable functional outcome (mRS 0–3 vs. 4–6) in interpreting the findings of the FINISH trial. The approach, to be used in the blinded data interpretation (BDI) [8] of the FINISH trial, is outlined below. In addition, in the event that we will observe a statistically significant difference in the number of deaths

between the two groups, we will carry out a detailed analysis of the causes of death by examining the official death certificates of the participants.

We will claim treatment non-inferiority only if:

- 1) Our primary efficacy analysis, based on the primary outcome, shows non-inferiority and the finding is supported both by the ITT and the PP analyses,
and
- 2) there are no relevant between-group differences in mortality (alive or dead at 6 months) or unfavorable functional outcome (mRS 0–3 vs. 4–6 at 6 months) between the groups (according to an approach outlined in the BDI).

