Summary statistics will be presented for both groups. Continuous variables will be presented in terms of mean values or medians with SDs and IQRs, respectively. Categorical variables will be presented with relative frequencies in percent.

The results from the statistical analysis will be considered to support a claim of non-inferiority if the upper limit of a one-sided 97.5% CI (or equivalently a 95% two-sided CI) excludes a difference in the primary endpoint in favor of the irrigation group of more than 7.5%. The center stratification of the randomization will be accounted for in the calculation of the CI.

Exploratory analyses of secondary and other binary endpoints will be performed using the χ^2 test or logistic regression analysis. Continuous outcomes will be analyzed using regression Student's t-test, analysis of covariance or regression models.

Potential effect modifiers will be analyzed by including interaction terms in statistical models for the following subgroups:

- patient age (<70 years, \geq 70 years)
- GCS score at baseline (9–12, 13–14, 15)
- history of head trauma (<4 weeks, \geq 4 weeks, head trauma with unknown timing, no head trauma)
- unilateral versus bilateral CSDH
- use of anticoagulation and/or antiplatelet medication versus none
- preoperative mRS (0–3, 4–5)
- hematoma density (isodense, mixed-density, hypodense)
- hematoma size (width in mm)
- presence of membranes on preoperative imaging (yes, no)

The primary endpoint will be investigated as described above using a CI, which is equivalent to using a non-inferiority test with a one-sided p-value of 0.025 (or a two-sided of 0.05). The between-group comparison of 6-month mortality and mRS 4–6 differences will be compared using 85% and 95% CIs (as outlined in more detail in the BDI). The statistical testing of other endpoints will also be performed using a two-sided significance level of 0.05.

STATA (Statistics/Data analysis, SE v15.1, StataCorp LLC, [name]) will be used for analyses.

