Given that the objective of surgery for CSDH extends beyond preventing reoperations to also encompass the improvement of neurological function and prevention of death, the entire treatment effect of intraoperative irrigation (versus no irrigation) may not be adequately captured by focusing solely on the primary outcome measure, the rate of reoperations. We deemed it crucial to also consider the potential impact of between-group differences in deaths and/or unfavorable functional outcomes, as both could have an effect on the rate of reoperations. We felt that in the name of transparency and trustworthiness, we would need to define *a priori* thresholds for between-group differences in mortality and rate of unfavorable functional outcome (mRS 4–6) at 6-months that we consider “concerning” or “alarming”.

We considered a difference to be “concerning” if the 85% confidence interval (CI) of the absolute between-group difference in mortality or rates of unfavorable functional outcome (mRS 4–6) did not encompass the value of 0.0 and “alarming” if the 95% CI of the absolute between-group difference in mortality or mRS 4–6 rates did not encompass the value of 0.0.

Prior to establishing the thresholds for the 85% CI (“concerning”) and 95% CI (“alarming”) thresholds, we conducted simulations to ensure that these thresholds would yield clinically relevant differences in mortality and unfavorable functional outcome (mRS 4–6) (Figure 4). For the mortality simulations, we assumed a mortality rate of 5% in the standard care group. This selection was based on two recent similar-sized RCTs, in similar settings (Sweden [11], UK [12]), where the 6-month mortality rate was 5% in the groups treated with burr-hole craniostomy and subdural drainage. As for the mRS 4–6 simulations, we assumed an mRS 4–6 rate of 10% based on the results of the DEX-CSDH [12] and DESCA trials [13].

[figure not shown]

Figure 4. Simulation of the 95% (left panel) and 85% (right panel) confidence intervals for between-group differences in 6-month mortality rates (upper panel) and rates of mRS 4–6 (lower panel). The difference in mortality and/or rates of mRS 4–6 is significant if the 85% CI or 95% CI does not encompass the value of 0.0.

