Acknowledging that the FINISH trial was not powered for assessing differences in mortality or rate of unfavorable functional outcome (mRS 4–6), we used a 3-level hierarchy (**low** / **moderate** / **high**) for expressing our confidence in the possible between-group differences according to the GRADE approach [14–16]. We assumed a 6-month mortality rate of 5% [12,17] and an mRS 4–6 rate of 10% [12]. In terms of **mortality**, the confidence in the estimate was considered **low** if the overall 6-month mortality rate was **<5%**, **moderate** if the overall 6-month mortality rate was **5–10%**, and **high** if the overall 6-month mortality rate was **>10%**. Regarding 6-month unfavorable functional outcome (**mRS 4–6**), the confidence in the estimate was considered **low** if the rate of mRS 4–6 was **<10%**, **moderate** if the rate of mRS 4–6 was **10–15%**, and **high** if the rate of mRS 4–6 was **>15%**.

Our scheme for interpreting the possible safety concerns is outlined in Tables 3 and 4.

Table 3. A priori set thresholds for **concerning** and **alarming** between-group differences in 6-month mortality with associated confidence estimates and pre-determined commitments for interpretation.

Overall mortality in whole population	Confidence in estimate	Threshold for relevant between-group difference in mortality	Resulting action if threshold fulfilled	Authors' interpretation commitment
<5%	Low	Concerning: The 85% confidence interval of the between-group difference in absolute mortality-% does not include 0.0	None	We refrain from making any comments due to the low event rate (low confidence in effect estimate).
		Alarming: The 95% confidence interval of the between-group difference in absolute mortality-% does not include 0.0	Notion on safety concern added to the discussion (not added to the conclusion).	Group A/B was associated with an alarmingly higher mortality rate. Given the event rate, the confidence in this finding was low .
5–10%	Moderate	Concerning: The 85% confidence interval of the between-group difference in absolute mortality-% does not include 0.0	Notion on safety concern added to the discussion (not added to the conclusion).	Group A/B was associated with a concerningly higher mortality rate. Given the event rate, the confidence in this finding was moderate .

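### The blinded interpretation scheme does not carry out condition 2 of the non-inferiority claim: section 3.2 makes it a bar, Tables 3 and 4 and Step 5 do not

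*SAP*

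**What the plan says.** The claim rule in section 3.2, copied into the change table of section 3.3, opens with "We will claim treatment non-inferiority only if" and then sets two conditions. The first is non-inferiority on reoperation in both ITT and PP. The second is that "there are no relevant between-group differences in mortality (alive or dead at 6 months) or unfavorable functional outcome" are present, as judged by the approach in the BDI. Section 3.2 adds: "The between-group comparison of 6-month mortality and mRS 4–6 differences will be compared using 85% and 95% CIs". It does not say which of the two levels decides condition 2.

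Section 4 (BDI) then provides:

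- **Step 3, definitions.** "We considered a difference to be “concerning” if the 85% confidence interval (CI) of the absolute between-group difference in mortality" or mRS 4–6 excludes 0. The label 'alarming' is used when the 95% CI excludes 0.
- **Tables 3 and 4.** Both tiers stand under one column heading, in Table 3 "Threshold for relevant between-group difference in mortality". Each tier is crossed with an event-rate band, and the result is only where a safety remark goes: nowhere, the discussion or the conclusion. For a concerning difference in the lowest band (mortality below 5%, mRS 4–6 below 10%) the action is 'None', with the commitment "We refrain from making any comments due to the low event rate (low confidence in effect estimate".
- **Step 3, NO/YES question.** It asks whether safety concerns are imbalanced and names no level. NO adds a sentence that there were no relevant differences. YES sends the reader to Tables 3 and 4.
- **Step 5.** The Non-inferior row prints the same non-inferiority sentence under 'No difference' and under 'Difference'. In the latter case a safety sentence is added only if the tables assign it to the conclusion.

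**The concern.** Condition 2 is half of the rule that decides the trial, and it is worded as a necessary condition. A reader who starts from section 3.2 concludes that a relevant mortality or mRS difference withdraws the claim. A reader who starts from Step 5 concludes that nothing found in Step 3 can withdraw it. Both follow the signed plan and reach opposite conclusions from the same data.

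The low event-rate band shows the conflict most sharply. There a concerning difference meets the tables' own threshold for relevance, and so fails condition 2, while the authors have bound themselves not to mention it. If section 3.2 governs, the claim is lost for a reason that may not be reported. If Step 5 governs, condition 2 does nothing.

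The BDI exists to fix the interpretation before the group labels are known, so the rule should leave no room for either reading.

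**Working it through.** **Inputs.** Recalculated size 289 per group (section 2.9.2). Mortality 5% and mRS 4–6 10%, the SAP's own simulation assumptions (BDI Step 3). Tiers at 85% and 95%, two-sided. Reoperation rate 9.6%, margin 7.5%, one-sided alpha 0.025, power 80% (section 2.9.1).

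**1. The plan's own figure.** The SAP states no error rate for condition 2. Its figure for condition 1 reproduces: n per arm = (1.960 + 0.842)² × 2 × 0.096 × 0.904 / 0.075² = 242.2, so 243. Then 2 × 243 = 486, and 486 / (1 − 0.157) = 576.5, taken up to 578, or 289 per arm.

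**2. The tiers are nested.** The critical values are 1.440 (85%, p < 0.15) and 1.960 (95%, p < 0.05). Every alarming difference is therefore also concerning. With both listed as thresholds for relevance, the literal entry level is 85%.

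**3. Smallest excess that triggers each tier.** Wald SE = √[p₁(1 − p₁)/n + p₂(1 − p₂)/n], n = 289.

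| Outcome | Reference arm | 85% reached at | 95% reached at |
|---|---|---|---|
| Mortality | 14 | 23 (3.1 points) | 26 (4.2 points) |
| mRS 4–6 | 29 | 41 (4.2 points) | 45 (5.5 points) |

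**4. A concerning difference in the low band.** 9 v 17 deaths of 289 each: overall 26/578 = 4.5%; difference 2.77 points; SE 1.72; z = 2.77/1.72 = 1.61, p about 0.11.
- 85% CI: 2.77 ± 1.440 × 1.72, about 0.3 to 5.2, excludes 0.
- 95% CI: 2.77 ± 1.960 × 1.72, about −0.6 to 6.1, includes 0.
- Section 3.2 with the Table 3 heading: relevant, claim barred.
- Table 3: action 'None', no comment.
- Step 5: non-inferiority sentence kept. If Step 3 is answered YES, no safety sentence follows. If it is answered NO, the conclusion says there were no relevant differences.

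**5. An alarming difference.** 14 v 26 deaths: overall 40/578 = 6.9%, moderate band; difference 4.15 points; SE 2.10; z = 1.97, so the 95% CI just excludes 0.
- Section 3.2: claim barred at either level.
- Table 3: safety remark in the conclusion.
- Step 5: non-inferiority sentence still printed, with the remark beside it.

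The conflict therefore does not depend on which tier is meant.

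**6. How often it matters by chance.** 400,000 simulated trials, both arms 5% dead, 5% alive with mRS 4–5 and 90% other; condition 2 fails if either outcome triggers in either direction, because its wording gives no direction.

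| Reading | Condition 2 fails |
|---|---|
| 85% CI is the bar | 23.7% |
| 95% CI is the bar | 8.4% |
| Step 5 governs | 0% (by construction) |

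From 243 to 294 per arm the first two rows range over 23.7–24.9% and 8.4–8.5%. Counting an excess in one given arm only, at 289, they are 11.9% and 4.2%. A mortality difference that is concerning but not alarming, with overall mortality below 5% as in step 4, occurs in 4.7% of trials.

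**The case against.** The strongest defence is that the scheme is deliberately graded and Step 5 is a fixed template. The primary result selects the row, and the tables select the safety sentence. The Step 5 sentence speaks only of preventing reoperations, so it could be taken as a narrower statement than the treatment claim in section 3.2. This does not rescue condition 2. Step 6 copies the final interpretation from Step 5, and no other place in the BDI tests or states the broader claim. A condition introduced with 'only if' would then have no effect anywhere. The template does mean that the non-inferiority sentence itself would not turn on a level picked at the meeting; only the answer to the unlevelled Step 3 question would.

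A reader might go further and infer that condition 2 is set at two competing levels, so that only results with p between 0.05 and 0.15 are affected. The SAP does not support that. The tiers are nested, the column heading makes 85% the literal entry level, and no place makes 95% the bar. Nor is the conflict confined to that band, as the alarming example shows.

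The Figure 4 caption is weak evidence too. "The difference in mortality and/or rates of mRS 4–6 is significant if the 85% CI or 95% CI does not encompass the value of 0.0" most naturally describes the figure's two panels, one per level; it says 'significant' rather than 'relevant' and does not mention condition 2.

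Finally, the SAP says that both thresholds were checked by simulation for clinical relevance. Agreement with the 0.05 level used for other tests does not show 85% to be wrong.

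**Conclusion.** The decision rule contradicts itself. Section 3.2 makes the absence of a relevant difference necessary for the claim. The literal threshold for relevance in Tables 3 and 4 is the 85% CI. The same tables attach no action to such a difference in the low band, Step 3 names no level, and Step 5 never withdraws the claim. This is more than missing detail, because the places give different answers for the same data.

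Depending on which place is followed, condition 2 fails by chance in about 24%, about 8% or 0% of trials with identical arms. These figures rest on Wald intervals without centre stratification, 289 per arm, the SAP's 5% and 10% rates, and ITT only. They do not add the per-protocol comparison of Table 6 and are not conditional on condition 1 being met. They show that the reading matters; they do not show which reading is right.

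**What to change.** Before the blinded meeting, reconcile sections 3.2 and 3.3, Step 3, Tables 3 and 4 and Step 5:

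1. State in one place whether a relevant difference withdraws the non-inferiority claim.
2. Name the single tier that answers both condition 2 and the Step 3 NO/YES question.
3. If a relevant difference does withdraw the claim, change the Step 5 cell for Non-inferior with Difference to say so. Replace any 'None' or no-comment entry for a difference that removes the claim, so that the reason is always reported.
4. If it does not, replace condition 2 in sections 3.2 and 3.3 with the reporting rule of Tables 3 and 4.

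Naming a tier without changing Step 5 would leave the contradiction in place. The choice between 85% and 95% is the sponsor's: a 95% bar is less sensitive to a real difference, and an 85% bar blocks the claim by chance more often. The Figure 4 caption need not change. The cost is wording only, with no new data, analyses or patients, and Tables 5 and 6 already report both intervals.

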2.2 Design, Monitoring and Timetable

In this national five-center, stratified, block-randomized (block sizes 4, 6, 8) trial we randomized 587 patients to undergo burr-hole craniostomy of a CSDH in a 1:1 ratio. We compared the effect of burr-hole craniostomy with intraoperative irrigation followed by 48h (± 12 h) subdural drainage (irrigation group) and burr-hole craniostomy without intraoperative irrigation followed by 48h (± 12 h) subdural drainage (no irrigation group) on symptomatic CSDH recurrence requiring reoperation over the course of 6 month follow-up.

The full study protocol of the FINISH study has been published [1]. The trial was designed and conducted by the FINISH investigators and the analyses were completed at the coordinating center. The trial protocol was approved by ethical review at the institutional review board of the Helsinki and Uusimaa Hospital District on November 13, 2019 (HUS/3035/2019) and duly registered at ClinicalTrials.gov (<https://clinicaltrials.gov/ct2/show/NCT04203550>). All participants provided written informed consent. The trial was monitored by Clinical Research Unit of the Helsinki University Hospital (HYKS Institute), Helsinki, Finland. The writing committee of the FINISH trial vouch for the accuracy and completeness of the data, the fidelity of the trial to the protocol, and the complete reporting of adverse events. There was no industry involvement in the trial.

The FINISH trial was launched in the coordinating center (Helsinki) on January 1st, 2020. Due to the Covid-19 pandemic, the next centers joined with some delay, as follows: Oulu University Hospital in July 2020; Kuopio University Hospital in August 2020; Tampere University Hospital and Turku University Hospital in October 2020. All study centers retained in the trial until patient recruitment was completed on August 17, 2022.

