2.3 Participants

During the recruitment period of the trial, we screened all patients with a symptomatic CSDH (CT or MRI verified) undergoing burr-hole evacuation in one of the study centers for trial eligibility.

The inclusion criteria were:

- Patients with a symptomatic unilateral or bilateral CSDH requiring burr-hole evacuation
 - o Patients with bilaterally operated CSDHs will be treated with the same protocol on both sides and analyzed as a single study participant
- Predominantly hypodense or isodense on CT imaging (or chronic hematoma on MRI)
- Clinical symptoms correlating with the CSDH
- Patients older than 18 years of age

The exclusion criteria were:

- CSDH requiring surgical treatment other than burr-hole evacuation (eg, craniotomy)

- CSDH in a patient with a cerebrospinal fluid shunt
- Patients who had undergone any prior intracranial surgery
- Comatose patients (Glasgow Coma Scale (GCS) score ≤ 8) with absent motor responses to painful stimuli; decerebrate or decorticate posturing), where rapid hematoma evacuation was required
- postoperative cooperation was suspected to be insufficient for drain usage (ie, disoriented or semiconscious patient)
- had received active treatment for a haematogenic malignancy within the previous 5 years
- Patients with a central nervous system malignancy or tumor that may cause the patient's current symptoms or may interfere with the operation (eg, a small incidental meningioma without associated brain edema, not in the vicinity of the planned burr hole, was not an exclusion criterion)
- acute infection that required antibiotic treatment
- high risk of life-threatening thrombosis (eg, recent coronary stent, intracranial stent, recent pulmonary embolism, low-pressure cardiac valve replacement [mitral or tricuspid valve replacement]) and discontinuation of antithrombotic medication was not recommended

Screening logs were kept at all five centers until the end of the study (August 17, 2022). After being fully informed of the trial protocol, 588 eligible patients willing to participate (written informed consent from patient or next-of-kin) were randomized.

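### The age interaction is tested with an unexplained cut at 70, which costs power if modification is roughly linear; the GCS 9–12 level also lacks a rule for sparse data

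*SAP*

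**What the plan says.** SAP section 3.2 (Final statistical analysis plan) sets out the method as follows: "Potential effect modifiers will be analyzed by including interaction terms in statistical models for the following subgroups". Three entries in the list that follows matter here.

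- Age has two levels. The entry begins "patient age (<70 years" and its other level is 70 and over.
- GCS has three levels: "GCS score at baseline (9–12, 13–14, 15".
- Haematoma size appears as "hematoma size (width in mm", with no categories.

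No reason is given for any cut-point, and there is no rule for a level with few patients or events. The type of model and the effect scale are not named. Section 3.1, which reproduces the original analysis plan, listed age and preoperative clinical status without categories. Section 3.3 discloses the change.

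Two exclusions in section 2.3 bear on the GCS levels. One removes "Comatose patients (Glasgow Coma Scale (GCS) score ≤ 8) with absent motor responses to painful stimuli". The other applies where "postoperative cooperation was suspected to be insufficient for drain usage (ie, disoriented or semiconscious patient". The SAP gives no distribution of age or baseline GCS. Its blank Table 1 has a row for GCS 9–12.

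**The concern.** Age is recorded in years. Cutting it in two treats everyone on the same side of 70 as alike, so a gradual change in treatment effect with age is harder to detect. Haematoma width, also continuous, is listed without a cut, and the SAP does not explain the difference.

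The secondary worry is the lowest GCS level. Some patients at GCS 9–12 are likely to be judged semiconscious or disoriented and so not enrolled. If few remain, an arm may have no reoperation at that level. In a logistic model fitted by ordinary maximum likelihood, the interaction coefficient for that level then has no finite estimate. Without a rule fixed beforehand, the analyst must decide how to handle it with the results in view.

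At stake is the usefulness of two exploratory interaction tests, not the trial's main claim.

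**Working it through.** **The plan's own figures.** The SAP states no power or sample size for interaction tests. The 9.6% reoperation rate used below comes from section 2.9.1, where the sample size reproduces:

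- (1.96 + 0.8416)² × 2 × 0.096 × 0.904 / 0.075² = 242.2, rounded up to 243 per group
- 243 / 0.90 = 270 per group
- 486 / (1 − 0.157) = 576.5, taken up to 578 in section 2.9.2, or 289 per group

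**Age.** Assume that age is normal and that modification is linear in age. Let q be the share of patients under 70 and z the normal quantile at q. The information kept by the two-level version, relative to continuous age, is φ(z)² / [q(1 − q)]. If the continuous test had 80% power at two-sided 5%, the power of the cut version is Φ(2.8016 × √efficiency − 1.96).

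| Share under 70 (assumed) | Calculation | Information kept | Power, if continuous has 80% |
|---|---|---|---|
| 20% | 0.2800² / 0.1600 | 0.49 | 50% |
| 25% | 0.3178² / 0.1875 | 0.54 | 54% |
| 50% | 0.3989² / 0.2500 | 0.64 | 61% |

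A median cut is the best case, so under these assumptions at least 36% of the information is lost wherever 70 falls in the age distribution.

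**GCS 9–12.** Let k be the number of patients per arm at this level, with a 9.6% reoperation rate in both arms. The chance of no event in at least one arm is 1 − (1 − 0.904^k)². With 289 per arm:

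| Share at GCS 9–12 (assumed) | k per arm | 0.904^k | Chance of no event in at least one arm |
|---|---|---|---|
| 3% | 9 | 0.403 | 64% |
| 5% | 14 | 0.243 | 43% |
| 8% | 23 | 0.098 | 19% |

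An arm without events is more likely than not only when 0.904^k exceeds 0.293. That means k of about 12 or fewer, a share of about 4%. At 29 per arm (about 10%) the chance is 10%.

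Sections 2.2 and 2.3 disagree on the number randomised ("we randomized 587 patients to undergo burr-hole craniostomy of a CSDH in a 1:1 ratio" against "588 eligible patients willing to participate"), which should be reconciled but hardly matters here. With 294 per arm, a 5% share rounds to 15 patients and the chance is 39%.

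Even an estimable term would say little. Assume 60% of patients at GCS 15 (176 per arm). The standard error of the log ratio of odds ratios, 9–12 against 15, is √[2/(k × 0.096 × 0.904) + 2/(176 × 0.096 × 0.904)]. This is 1.29 for k = 15 and 0.96 for k = 29. The ratio detectable with 80% power, exp(2.8016 × SE), is about 37 and 15. These are rough figures, since the normal approximation is poor with so few events.

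**The case against.** The strongest reply on age is that nothing promised was withdrawn. The original plan named age without a functional form, so the final plan closes an open choice in advance and discloses it. The list is headed as subgroups, two age groups are easy to read, and a true threshold near 70 would cost little. All of this stands. It shows that the cut is neither a contradiction nor an undisclosed change. It does not show that the cut is the better test when the shape of any modification is unknown. Nor does the SAP say outright that width will be modelled as continuous, so the contrast is an unexplained difference and no more.

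On GCS, a reader might infer that the entry criteria nearly empty the 9–12 level, or that its interaction cannot be estimated. The documents do not support either reading:

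- The coma exclusion stops at GCS 8.
- The other exclusion is a judgement about cooperation, not a GCS cut, and disoriented patients may equally be at GCS 13–14.
- Table 1 plans a 9–12 row.
- No GCS counts are given, and the chance of an arm without events falls from 64% to 19% over the assumed shares alone.
- The interaction model is not fixed as logistic. A risk-difference interaction can be computed with an empty cell, and a likelihood-ratio test stays finite even when one logistic coefficient diverges.

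A reader might also infer that enrolled patients at GCS 9–12 are entry violations and leave the per-protocol set. Sections 2.3 and 3.2 do not say so.

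**Conclusion.** The point holds for age, as a modest improvement. With a linear modifier and normal age, both assumed, the cut keeps about 49% to 64% of the information when 20% to 50% of patients are under 70. Where a continuous test would have 80% power, it leaves about 50% to 61%. It would be wrong to say that half the information is lost whatever the circumstances, because the loss depends on an age distribution and a shape of modification that the SAP does not give.

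For GCS, what holds is narrower: the lowest level may be thin, by an amount the documents do not show, and no rule says what happens if it is.

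Neither part touches the main conclusion. Under section 3.2 the non-inferiority claim rests on the primary outcome in the ITT and PP analyses, together with mortality and mRS. No effect-modifier result enters the blinded interpretation steps.

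**What to change.** **Age.** Test the age-by-treatment interaction with age as a continuous variable, and keep under 70 / 70 and over for display only. The cost is an assumption of rough linearity, which the displayed groups let readers check.

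**GCS.** Keep the three levels by default. State in advance that 9–12 is merged with 13–14 for the interaction test if the pooled, blinded number of patients or events at that level falls below a stated minimum. Report counts by arm for all three levels in any case. The minimum should be written into the SAP. As a guide, 58 patients pooled (29 per arm) gives about a 10% chance of an arm without events at a 9.6% rate. A conditional rule is preferable to collapsing the levels outright, which would hide a difference confined to the lowest band even if the numbers turn out adequate. The merge has the same drawback, but only where the data could not have shown such a difference.

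Both changes are SAP wording only. Pooled counts do not reveal allocation, so the rule can be applied without breaking the blind.
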